- c) Any differences in outcomes (BRIEF2/P, GNG, HCU) between children randomized to eAT or to WWS will not vary by age, baseline overweight/obesity, atopy/asthma status, secondhand smoke exposure, family and neighborhood socioeconomic status, family functioning, baseline symptom severity (i.e., Sleep Disordered Breathing Scale) or race (African American vs other; Minority vs. non-minority).

Exploratory Analyses

Analyses addressing secondary hypotheses will be considered exploratory. These include mediation and moderation analyses.

As snoring is the focus of this study, we will assess the association between quantitative estimates of snoring with study outcomes at baseline, evaluate the treatment effect on these snoring measurements, and whether changes in snoring correlates with changes in study outcomes, as an exploratory analysis.

Variables Used to Stratify Randomization

Randomization will be stratified by the following factors within site: age (\leq 5 years vs $>$ 5 years); overweight status (body mass index [BMI] $>$ 85%ile); and race (African American vs other). These represent key groups likely to influence treatment responses.

Stratification by these factors will provide greater assurance that the comparison groups will be similar with respect to these and related variables. Given an overall sample size of 460 and a relatively large number of strata (8 strata within each of the 5 sites), we will use a dynamic randomization method, Pocock and Simon's minimization method⁷¹, implemented in the Data Management System (Slice), to ensure treatment arms are balanced with respect to these factors as well as for the number of subjects in each group. Because the minimization method is more complex than stratified permuted blocks, [name] will monitor the randomization assignment closely to ensure the integrity of randomization.

Estimated Power and Sample Size

The study plans to randomize 460 subjects into one of the two arms in a 1:1 ratio. Based on the experience in the CHAT study, we assume a dropout rate of 15% at 6 months, and an additional 5% attrition at 12 months, resulting in 390 and 368 evaluable subjects at 6 and 12 months, respectively. As described below, this sample size was chosen so that the study will have ample power to detect moderate to large moderation effects and a range of mediation effects when the exposure-moderator and moderator-outcome associations are moderate or large.

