To compare changes in the BRIEF2/P GEC score and GNG score at 6 and 12 months in the eAT and WWSC groups, we will perform a longitudinal analysis with time (0, 6, and 12 months) as a categorical variable, and with the assumption of equal means at baseline to reflect the randomized design. Both visit and treatment group will be treated as categorical variables to allow separate comparisons of intervention groups at 6 and 12 months. This analysis will also permit testing of the null hypothesis that the means of changes in BRIEF2/P scores and GNG scores at 6 and 12 months are the same in the eAT and WWSC groups. The model and testing procedure are:

Let X_1 and X_2 be indicator variables for time = 6 months and time = 12 months, and let X_3 be the indicator variable for treatment group. We will fit a mixed effects model for repeated measures that includes the main effects of X_1 and X_2 , and the interactions between X_3 and the two indicator variables for time, X_1 and X_2 . Let β_3 and β_4 denote the coefficients of the interaction terms $X_1 \times X_3$ and $X_2 \times X_3$, respectively. β_3 and β_4 represent the treatment effects at 6 and 12 months and the average treatment effect is given by $(\beta_3 + \beta_4)/2$. Standard methods will be used to estimate and test the null primary hypothesis of $\beta_4 = 0$.

Comparisons will be adjusted for stratification factors, and as appropriate, adjusted for potential covariates found to differ between groups at baseline and for baseline levels of other relevant covariates. Because the GNG test versions were developed for three broad age groups (with increasing difficult with higher age) we will address statistical adjustments that may be needed to accommodate heterogeneity in test difficulty across versions.

Secondary Analyses

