Aim 2: For endpoints related to HCU (illness or injury requiring hospitalizations; emergency department visits; inpatient procedures; outpatient procedures; scheduled office visits; unscheduled office visit or urgent care visits; medication use), incidence rate per person will be calculated. Recognizing that these count data are likely to be non-normal and skewed, we will use Wilcoxon rank-sum tests to compare study groups. To better model the underlying distribution of the count data and take into account potential data dispersion and possible preponderance of zeros, we will use goodness of fit statistics (e.g., AIC/BIC), likelihood ratio tests or the Vuong test⁸² to choose among the zero-inflated negative binomial models, zero-inflated Poisson models or regular negative binomial models. The models that best fit the data will be used to model treatment effect adjusting for covariates. Incidence rate ratios comparing treatment groups will also be reported. We also will describe distributions of medication classes (e.g., antibiotics, nasal anti-inflammatory medications, asthma medications) and reasons for hospitalizations, etc. by group to identify reasons for HCU differences (e.g., infection; respiratory illness). Analyses will be performed both including and excluding events associated with the intervention (surgery and pre- and post-operative care, but not include the polysomnography).

Aim 3: Whether treatment effects pertain to some subgroups and not to others are of great clinical significance. Statistical tests of treatment by covariate interaction will be performed to assess whether treatment effect varies by age, baseline weight, atopy/asthma status, secondhand smoke, socioeconomic status, family functioning, baseline symptom severity (e.g., Sleep Disordered Breathing Scale) or race. Within the group of children with asthma, we will assess whether asthma exacerbations differ by treatment group, using similar approach for count data as described in the analysis for HCU indices.

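### Allocation is minimised on site, age, overweight and race, but the Aim 2 count tests are plain Wilcoxon tests; if those factors predict utilization, the tests are conservative, and adjusting costs almost nothing

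*Combined protocol and SAP*

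**What the plan says.** All references are to section 19, Statistical Analysis Plan.

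- **Allocation** (Variables Used to Stratify Randomization): "Randomization will be stratified by the following factors within site: age", followed by overweight and race. With many strata, "we will use a dynamic randomization method, Pocock and Simon's minimization method". On the choice of factors: "These represent key groups likely to influence treatment responses".
- **Co-primary outcomes** (Statistical Approaches to Testing for Treatment Differences): directly after the mixed model for BRIEF2/P and Go-No-Go, "Comparisons will be adjusted for stratification factors".
- **HCU counts** (Secondary Analyses, Aim 2): "Recognizing that these count data are likely to be non-normal and skewed, we will use Wilcoxon rank-sum tests to compare study groups". No stratification or adjustment is attached to this test. The plan then chooses the best-fitting zero-inflated or negative binomial model, uses it to estimate the treatment effect with adjustment for unspecified covariates, and reports incidence rate ratios.
- **Asthma exacerbations** (Secondary Analyses, Aim 3): compared between arms "using similar approach for count data as described in the analysis for HCU indices".
- **Power** (Estimated Power and Sample Size): the Aim 2 and asthma-exacerbation power figures are based on the two-sided Wilcoxon test at 5%.
- **Status** (Exploratory Analyses): analyses of secondary hypotheses are exploratory.

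**The concern.** Minimisation makes the arms more alike on the balancing factors than simple randomization would. The difference between arms in any outcome that depends on those factors therefore varies less from trial to trial. The plain Wilcoxon variance is derived as if allocation were completely random, so it still includes the variation that the design has removed. The standard error is then too large, the test rejects a true null less often than 5%, and power falls below what an analysis using the same factors would give.

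The co-primary analysis avoids this by adjusting. For Aim 2, neither analysis is guaranteed to: the Wilcoxon test is unadjusted, and the count model has unnamed covariates. At stake is a real but modest utilization difference, or a modest fall in exacerbations, that the trial could have detected and does not.

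**Working it through.** **Inputs from the plan.** "The study plans to randomize 460 subjects into one of the two arms in a 1:1 ratio"; "we assume a dropout rate of 15% at 6 months, and an additional 5% attrition at 12 months". Evaluable: 460 × 0.80 = 368, or 184 per arm. Asthma subgroup: 110 evaluable. The power section anticipates 50% of children under 5 years, 47% overweight or obese and 40% African American. Two-sided 5%.

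**Inputs that must be assumed.** The documents do not give the minimisation assignment probability (taken as 0.8) or how strongly the factors predict counts (a range is used). The analysis plan says 5 sites and the study summary says 7. Both were used, and the direction does not change.

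**Step 1: the plan's own power figures.** Monte Carlo with a tie-corrected Wilcoxon test and no factor effects:

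| Comparison | Plan | Recomputed |
|---|---|---|
| Hospitalizations, Poisson 0.06 vs 0.25 | >99% | 99.8% |
| Consultations, Poisson 1.9 vs 3.5 | >99% | 100% |
| Asthma exacerbations, 1.3 vs 4.1 (also 1.8 vs 4.1) | >99% | 100% |
| Emergency visits, 0.35 vs 0.37 | limited | 6% |
| Asthma, 27% reduction from 4.1 | 80% | 84% |

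The last figure is slightly conservative in the plan: 80% power is reached at a reduction of about 25.5%.

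**Step 2: mechanism.** Let R² be the share of the variance of the ranks explained by the four factors. If allocation balanced them perfectly, the true variance of the rank-sum difference would be (1 − R²) times the one the plain test uses. Then

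- null rejection = 2Φ(−1.96/√(1 − R²));
- plain power, where the adjusted test has 80% = Φ(1.96 + 0.84 − 1.96/√(1 − R²)).

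| R² (assumed) | 1.96/√(1 − R²) | Null rejection | Plain power (adjusted 80%) |
|---|---|---|---|
| 0 | 1.960 | 5.0% | 80% |
| 0.1 | 2.066 | 3.9% | 77% |
| 0.2 | 2.191 | 2.8% | 73% |
| 0.3 | 2.343 | 1.9% | 68% |

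Real minimisation balances less than perfectly, so these are approximate upper bounds on the loss.

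**Step 3: simulation at an assumed rate ratio of 0.75**, 368 analysed, plain Wilcoxon against an analysis adjusted for the balancing factors.

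| Factor effects | Power, 7 sites | Null, 7 sites | Power, 5 sites | Null, 5 sites |
|---|---|---|---|---|
| None | – | – | 76 vs 76% | 5.1 vs about 5% |
| Weak | 77 vs 79% | 4.5 vs 5.0% | 73 vs 75% | 3.6 vs about 5% |
| Moderate | 72 vs 80% | 3.3 vs 4.9% | 67 vs 73% | 3.8 vs about 5% |
| Strong | 67 vs 80% | 2.0 vs 4.5% | 61 vs 72% | 3.5 vs about 5% |

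The 7-site runs use negative binomial counts with mean 3 and shape 2. Site SD, age and race effects on the log scale are 0.2/0.3/0.2 (weak), 0.4/0.5/0.3 (moderate) and 0.5/0.7/0.4 (strong). The adjusted test there is ranks regressed on arm, site, age, overweight and race. The 5-site runs draw 368 analysed children from 460 minimised.

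Losses for moderate to strong effects: 73 − 67 = 6, 80 − 72 = 8, 72 − 61 = 11 and 80 − 67 = 13 points.

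**Step 4: the plan's own effects, with prognostic factors.** 5 sites; rate ratio per binary factor 1.00 / 1.35 / 1.82; top against bottom site 1.00 / 1.82 / 3.32. Plain against rank-adjusted power:

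- hospitalizations: 99.7 vs 99.7, 99.8 vs 99.8, 99.5 vs 99.7%;
- consultations: 100 vs 100% throughout;
- asthma 4.1 to 1.8: 100 vs 100, 100 vs 100, 99.1 vs 100%;
- asthma, 27% reduction: 83–85 vs 82–85, 70 vs 81–83, 38–41 vs 71%;
- emergency visits, 0.37 vs 0.35: about 5–7% with either test.

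Null rejection of the plain test with Poisson counts was 4.4, 3.4 and 0.6% at n = 368, and 5.2, 4.2 and 3.0% in the asthma subgroup. The 0.6% belongs to the extreme case, with strong effects and no overdispersion.

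**The case against.** A reader might infer that Aim 2 rests on unadjusted tests alone. It does not: the same paragraph plans covariate-adjusted count models with rate ratios, and asthma exacerbations inherit them. The adjustment sentence quoted for the co-primary outcomes also stands under a general heading on testing treatment differences, which makes the balancing factors the natural reading of the unnamed covariates. This stands in part. But that sentence follows the co-primary model and is not repeated for Aim 2, the model family is chosen from the data, and nothing says which result governs.

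A reader might also infer that the p-values are certainly too large and that power is certainly lost. The documents do not support that. The sentence on key groups speaks of treatment response, not of prognosis. In the Significance section (Health Care Utilization), the larger cost fall in the youngest children is likewise a change after surgery, and the remark about US patterns concerns a foreign sample, not differences between trial sites. How strongly the factors predict counts is an assumption throughout.

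Three further limits stand. At the planned hospitalization and consultation effects adjustment changes nothing of note. Asthma is not a balancing factor, so balance in that subgroup is looser and the conservatism smaller (null rejection 4.2% against 3.4% in the full sample, at a rate ratio of 1.35 per factor). And the plain test does not lead to an understated effect, because the effect estimates come from the count model.

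Against this, the planned effects come from uncontrolled data in children with frank sleep apnea, and the protocol notes that utilization appears lower in milder disease. Effects small enough for adjustment to matter are therefore plausible.

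**Conclusion.** The point holds as a minor one. After minimisation, the plain Wilcoxon tests for HCU counts and asthma exacerbations are conservative if site, age group, overweight or race predict those counts. With an assumed rate ratio of 0.75, the loss is about 2 points of power for weak factor effects and 6 to 13 points for moderate to strong ones; in the moderate to strong cases null rejection is about 2 to 4%. It is nil if the factors are not prognostic and negligible at the planned hospitalization and consultation effects. The plan's figure most exposed is the 27% reduction in asthma exacerbations: about 70% power plain against 81–83% adjusted, if each binary factor carries a rate ratio of 1.35 and the top site has 1.82 times the rate of the bottom site.

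These sizes rest on the assumed prognostic strengths, assignment probability and count distributions. No false-positive risk arises, and the analyses are exploratory.

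**What to change.** In Secondary Analyses, Aim 2, and by reference for asthma exacerbations in Aim 3:

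1. Name site, age group, overweight and race as fixed covariates in the count model that gives the rate ratios.
2. State that the inferential test is adjusted for these factors, and choose in advance which one it is: the treatment term of that model, or a rank analysis with the four factors as main effects.
3. Keep the plain Wilcoxon test as descriptive.

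Either test recovers the loss. In one comparison at a rate ratio of 0.75 (weak, moderate and strong effects) the adjusted negative binomial model had 83, 83 and 81% power against 76, 73 and 73% for rank regression. The dispersion was treated as known there, which favours the model. The rank analysis does not depend on the data-driven choice of count model.

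The cost is one or two sentences. The factors are already recorded for allocation, no new data are needed, and in the 5-site simulation with non-prognostic factors adjustment cost no power (76% with either test).

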difference in change score from baseline to 6-month in the BRIEF GEC score in the eAT group compared to the WWS group was 3.7 points. The standard deviation at baseline in the WWS group was 11.5 and the correlation between the baseline and the follow-up GEC score was 0.73. For the GNG score, the anticipated treatment difference is 0.33, based on a published study that found a difference between 5-year-old with vs without SDB on an objective attention test⁷⁴. In a study of 105 5-year old children studied with the GNG test at baseline and then 12 months later⁷⁵, Co-I [name] observed the baseline GNG score to have a standard deviation of 0.77 and to correlate with the 12-month follow-up score with an $r=0.48$. Using these estimates and methods described in Hedeker *et al* for sample size estimation for longitudinal designs with attrition, our sample size with the assumed attrition rate has 98% power to detect a difference of 3.7 points in the BRIEF2/P GEC change score and 98% power to detect a difference of 0.33 points in the GNG change score between treatment groups at a significance level of 2.5% and 5% respectively (the comparison for the BRIEF2/P GEC change score corresponds to a larger standardized effect and therefore is tested at a lower significance level of 0.025). The minimal effect size the study has 80% power to detect is 0.22 (0.24) for the GNG change score, and 2.4 (2.6) for the GEC change score at 5% (2.5%) significance level.

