Aim 3 is to identify factors that moderate the behavior and health care utilization changes in response to surgery (AT). As described in the CCC application, we anticipate that 50% of children will be age less than 5 years; 47% will be overweight/obese; 40% will be African American (AA), 30% will have asthma, and 20% will be exposed to secondhand smoke. The study will have 80% power to detect a treatment effect difference of 0.58, 0.59, 0.60, 0.64, and 0.74 standard deviations for interactions between treatment and age, overweight/obese, race, asthma, and secondhand smoke, respectively. In the CHAT study, the estimated difference in treatment effect on BRIEF

GEC score between AAs and non-AAs was 4.63 and the estimated standard deviations in the 4 subgroups defined by treatment and race ranged from 7.69 to 9.27. Assuming that the difference in treatment effect between AAs and non-AAs is 4.63 and a standard deviation of 9, a sample size of 184 per treatment group with 40% AAs provides 67% power to detect this difference (a 0.51 standard deviation of treatment effect difference) based on normal approximation at the 5% significance level.

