If we observe differences in behavior and vigilance between groups, we will determine whether improvements in vigilance explain a significant portion of the improvement in behavior, using the steps to establish mediation outlined by Baron and Kenny⁸⁴, which consist of fitting a series of regression models and testing relations among variable corresponding to significance tests of the regression coefficients. Specifically, we will construct regression models with change from baseline to 12 month BRIEF2/P GEC score as the outcome, including a treatment indicator as an independent variable, with and without including the change in the Go-No-Go performance test as a covariate. We will compare the coefficients for the treatment indicator to examine how much of treatment effect on the BRIEF2/P is explained by changes in the GNG test. Point and interval estimates for the reduction in the coefficients will be provided. Similarly, if sleep duration (by actigraphy and parent report) and sleep-quality (by PSG and parent report) demonstrate treatment effects, we will explore these factors as potential mediators for changes in behavior and vigilance (if these outcomes show treatment effects).

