If we identify race differences in treatment effects, we will explore whether those differences are explained by the measured social and environmental factors, such as measures of family functioning or secondhand smoke exposure. To address this question, we will use models similar to the mediated baseline by treatment interaction models proposed by Baron and Kenny⁸⁴ and MacKinnon⁸⁶, except that the mediators under consideration will be those measured social and environmental factors mentioned above. More specifically, we will fit the following models: (1) $Y = i_1 + c_1 X + c_2 Z + c_3 XZ + e_1$; (2) $Y = i_2 + c'_1 X + c'_2 Z + c'_3 XZ + bM + e_2$; (3) $M = i_3 + a_1 X + a_2 Z + a_3 XZ + e_3$, where Y denotes the outcome (e.g., BRIEF2/P GEC change score or GNG change score), X denotes the

treatment indicator, Z denotes race, and M denotes the potential mediator (measured social and environmental factor under consideration) for the racial differences in treatment effects (c_3). Our interest here is to explore the potential mediation effects corresponding to the effect of XZ to M to Y, through evaluating the significance tests for \hat{c}_3 , \hat{a}_3 , \hat{b} , and \hat{c}_3 (or $\hat{a}_3\hat{b}$), the estimates of corresponding regression coefficients.

One gap in the CHAT study was lack of objective data on nightly sleep duration, which may significantly influence behavior and cognition. In this study, we will evaluate whether baseline average nightly sleep duration and continuity obtained from in-home actigraphy are associated with: a) baseline behavior and performance measures; b) whether there is an interaction between sleep duration and treatment. Models will be similar to those described above. We also will evaluate whether changes in sleep duration and continuity are associated with changes in behavior and performance outcomes.

Impact of Coronavirus Disease 2019 (COVID-19) Pandemic

We will summarize data quality and missingness by whether the relevant visit (at baseline, 6 months, or 12 months) occurred (or was scheduled to occur) prior to or following 03/11/2020, the date on which the World Health Organization declared COVID-19 to be a global pandemic.

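### The written race-moderation and vigilance-mediation regressions use the 12-month change score without the baseline score, giving up precision that costs nothing to recover

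*Combined protocol and SAP*

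**What the plan says.** All references are to section 19 (Statistical Analysis Plan).

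- **Primary model** (Statistical Approaches to Testing for Treatment Differences). Baseline GEC or GNG is a response with a common mean in both arms, and a following sentence adds the stratification factors as adjustments.
- **Aim 3 interaction tests** (Secondary Analyses). "Statistical tests of treatment by covariate interaction will be performed to assess whether treatment effect varies by age", followed by the other moderators. No equation or adjustment set is given.
- **Aim 3 race models** (Secondary Analyses). If a race difference in treatment effect is found, three models are fitted. Model (1) regresses Y on treatment X, race Z and XZ. Model (2) adds a mediator M. Model (3) regresses M on X, Z and XZ. The outcome is defined by "where Y denotes the outcome (e.g., BRIEF2/P GEC change score or GNG change score". The XZ coefficient c3 in model (1) is the racial difference in treatment effect, and its significance test is listed.
- **Aim 1 vigilance mediation** (Secondary Analyses). "we will construct regression models with change from baseline to 12 month BRIEF2/P GEC score as the outcome", with treatment as a regressor, once with and once without the GNG change.
- **Power** (Estimated Power and Sample Size). The race interaction on GEC is given 67% power, with 184 children per arm of whom 40% are African American. The effect and spread behind that figure are stated as follows: "Assuming that the difference in treatment effect between AAs and non-AAs is 4.63 and a standard deviation of 9". For the five moderators the plan claims "80% power to detect a treatment effect difference of 0.58, 0.59, 0.60, 0.64, and 0.74 standard deviations". For GEC, "the correlation between the baseline and the follow-up GEC score was 0.73"; for GNG the baseline-to-12-month correlation is 0.48.

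**The concern.** Analysing a raw change score fixes the slope of follow-up on baseline at 1. The plan's own correlations, 0.73 and 0.48, imply slopes below 1 when the SDs are similar, so removable baseline noise stays in the residual. Because treatment is randomized, baseline is balanced in expectation between arms within each race group. Adding it leaves the XZ contrast unbiased and shrinks its standard error.

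This matters most where power is thinnest. The SAP gives power for moderation as a reason for the sample size, yet states only 67% for race. The Rationale section reports that the race finding in CHAT held after control for baseline behavioral scores; model (1) asks the same question without them. For the other moderators, an unstated model also leaves the adjustment open to choice after results are seen.

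**Working it through.** **1. Reproduce the plan's figures.** The 4.63 points come from the BRIEF row of Table 1: (−1.82 + 0.30) − (−4.98 − 1.17) = −1.52 + 6.15 = 4.63. The SDs of 7.69 to 9.27 behind the assumed SD of 9 are the change-score SDs in that row, so the stated power matches an unadjusted change-score analysis.

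With 184 per arm and moderator prevalence p, SE = SD × √[2 × (1/(184p) + 1/(184(1−p)))].

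For race, p = 0.40: SE = 9 × √[2 × (1/73.6 + 1/110.4)] = 9 × 0.2128 = 1.915. Power = Φ(4.63/1.915 − 1.96) = Φ(0.457) = 67.6%. The plan says 67% (0.51 SD gives 66.9%).

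The same formula gives 80%-power interactions of 0.584, 0.585, 0.596, 0.637 and 0.730 SD, against the stated 0.58, 0.59, 0.60, 0.64 and 0.74.

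**2. Effect of adding baseline.** With equal SDs s at both times and correlation ρ, the change score has residual variance 2s²(1−ρ) and the baseline-adjusted score s²(1−ρ²). The ratio is (1+ρ)/2.

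- GEC: 1.73/2 = 0.865, a fall of 13.5%; SD ratio 0.930.
- GNG: 1.48/2 = 0.74, a fall of 26%; SD ratio 0.860.

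**3. GEC race interaction.** Adjusted SD = 9 × 0.930 = 8.37. Power = Φ(2.417/0.930 − 1.96) = Φ(0.639) = 73.9%, a gain of 6.2 points. Simulation (4,000 runs): 67.2% to 72.7%.

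Sensitivity:

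| Input varied | Change score | Baseline-adjusted |
|---|---|---|
| ρ = 0.60 (change SD held at 9) | 67.6% | 77.1% |
| ρ = 0.80 (change SD held at 9) | 67.6% | 72.2% |
| Change SD 7.69 | 80.8% | 86.0% |
| Change SD 9.27 | 65.1% | 71.3% |
| SD 11.5 and ρ 0.73 (change SD 8.45) | 73.1% | 79.0% |

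**4. GNG.** The documents give no GNG interaction effect, so one must be assumed.

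| Assumed interaction | Change score | Baseline-adjusted | Gain | Simulation |
|---|---|---|---|---|
| 0.51 SD (the GEC race effect) | 66.9% | 79.6% | 12.7 points | 66.5% to 78.9% |
| 0.60 SD (80%-power race effect) | 80.5% | 90.6% | 10.1 points | 81.4% to 90.7% |

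**5. Equal-SD assumption.** For unequal SDs s0 (baseline) and s1 (follow-up), the change-score variance exceeds the adjusted variance by (s0 − ρs1)². Adjustment therefore never raises the residual variance. The gain vanishes only if s1 = s0/ρ, that is, if the follow-up SD is 1/0.73 = 1.37 times the baseline SD for GEC, or 1/0.48 = 2.08 times for GNG.

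**The case against.** The strongest reply is that the SAP's equations are schematic. The primary model's equation also lists only time and time-by-treatment terms; the stratification factors come in a later sentence, which also allows baseline levels of other relevant covariates. Absence from the race equations need not mean exclusion. And where the SAP writes out effect modification of the co-primary result, in the COVID-19 section, it extends the primary mixed model, which handles baseline properly.

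Much of this stands. A reader might infer that every Aim 3 moderation test is an unadjusted change-score regression. The documents do not support that: the race models are fitted only if a race difference appears, and the general interaction tests have no stated model. The power calculation's change-score SD does not settle it, since the co-primary endpoints are also described as changes yet analysed by mixed model. The cross-reference for sleep duration does not settle it either, because it also covers associations with baseline measures, where a change-score outcome cannot apply.

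A reader might also infer that no stratification factor is present. Race is one, and it is in the models as Z.

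What remains is that the adjustment sentence precedes the Secondary Analyses heading and is not carried forward, and that the race and vigilance regressions, as specified, use change scores and name no baseline term.

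**Conclusion.** The point holds for the regressions the SAP spells out: race models (1) and (2), and the vigilance-mediation pair. For the other Aim 3 interactions the defect is an unstated model.

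The size is about 6 power points for the GEC race interaction (67.6% to 73.9%; 72% to 77% adjusted for ρ from 0.80 to 0.60). It rests on equal SDs at the two times, a common correlation across arms and races, and a 6-month CHAT correlation applied at 12 months. For GNG the gain is roughly 10 to 13 points, but a flat figure would be unsupported: the interaction effect is assumed, and the 0.48 comes from 105 five-year-olds while the trial spans ages 3 to 12 with three test versions. The value of adding age, overweight status and site cannot be computed from the documents.

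It would be wrong to read this as bias. The randomized XZ contrast is unbiased either way, and the SAP labels moderation and mediation as exploratory. The change is worth making because it is cheap; the co-primary analysis is unaffected.

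**What to change.** State one interaction model for GEC and GNG in the Aim 3 text, by either route:

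1. **Extend the primary mixed model** with moderator, moderator-by-visit and moderator-by-treatment-by-visit terms, keeping equal arm means at baseline within each moderator level, and test the 12-month three-way term. The COVID-19 sensitivity model already has this structure.
2. **Add the baseline score, age, overweight status and site** to race models (1) and (2), and the same covariates to model (3). All three must share one covariate set, or the identity c3 − c3′ = a3·b, on which the mediated share rests, no longer holds exactly. If M is a follow-up measure, add baseline M, where collected, to all three.

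In the vigilance mediation, add baseline GEC to both regressions, and baseline GNG to both because GNG change is the covariate being added.

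The cost is SAP wording. A change score already requires the baseline value, so no child is lost by also using it as a covariate, and section 2.4.2 makes the parent BRIEF2/P mandatory before randomization. The one downside is that the race main effect c2 becomes conditional on baseline, which the SAP should say; c3 keeps its meaning.
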